Safety data will include performance on psychological screening tests, cognitive tests, and motor tests. Efficacy data will include performance on cognitive tests. All data will be reviewed by a safety committee as described above. If any patient develops motor effects that are uncomfortable, the study will be halted for that particular subject. Furthermore, if the patient develops worsening psychological effects as measured through psychological screening tools, the study will be halted and the patient will be referred for appropriate care through the departments of Psychiatry and Neurology at UC Davis.

Safety information will be collected at study visits and with a telephone call. It will be saved in the database established for this study.

Safety data for motor effects will be collected prior to the patient's surgery and at the final study visit. Psychological data will be collected prior to DBS placement, at the first study visit, by phone call during the sustained frequency stimulation period, and at the final clinic visit.

The principal investigator and study members will review the data after each clinic visit and telephone contact with the patient. A safety committee will review the data after the first 4 patients, 8 patients, 12 patients, and 20 patients. The committee will include the PI, [name] in addition to [name], [name], and [name]. [name] is a neurologist, co-director of the DBS group, and has participated in multiple clinical trials involving the Parkinson's disease population. [name] is an expert in neurocognitive assessment in Parkinson's disease and has experience in identifying study related neurocognitive effects in clinical trials in dementia.

Data will be analyzed and evaluated in cohorts of 4 patients through the first 12 patients to determine whether subjects remain safe. This means we will evaluate the safety data from the first 4 patients before proceeding with subsequent subjects. We will evaluate data again after a total of 8 patients, 12 patients, and 20 patients.

PROTOCOL TITLE: Safety and feasibility of using low frequency deep brain stimulation of the subthalamic nucleus to improve cognitive performance in patients with Parkinson's disease

Safety Data Analysis: To examine possible effects on motor symptoms, we will screen for significant changes in the motor section of the UPDRS score after sustained LFS. After each patient is tested, we will calculate individual changes in UPDRS scoring. After the entire patient population is tested, we will use a T-test to determine if there is a significant change the motor section.

We will also examine changes in psychological symptoms using the BDI and NPI. We will examine percentage of people who convert to moderate depression as indicated by a BDI score 20 or higher. We will also look for significant changes in the BDI and NPI across time using ANOVAs.

Changes in cognition will also be analyzed by looking at reaction time and error rates on different cognitive tests as described previously.

- Any conditions that trigger an immediate suspension of the research.

None.

16) Withdrawal of Subjects

Describe anticipated circumstances under which subjects will be withdrawn from the research without their consent.

Patients unable to perform cognitive tests due to effort or altered mental status.

Patients who experience any change in psychological symptoms that is concerning to the patient, caregiver, or test administrator as assessed through psychological screening tools.

Describe any procedures for orderly termination.

The patient is not undergoing any additional procedures, except for stimulation and cognitive testing.

Describe procedures that will be followed when subjects withdraw from the research, including partial withdrawal from procedures with continued data collection.

Patients' data will be recorded, unless specifically asked to be withdrawn

Patients will continue to be followed for medical management

17) Risks to Subjects

Physical Risk:

- There is minimal to no physical risk. Once the patient's stimulation is turned off, the patient's pre-stimulation symptoms will likely return (Temperli et al 2003).
- There is a small chance that changes in affective symptoms including dysphoria, depression, mania, or psychosis may occur (Smeding et al 2006, Strutt et al 2012). Patients will be carefully screened using standardized assessment tools.
- All cognitive and memory tests are designed to be minimally difficult and pose minimal

PROTOCOL TITLE: Safety and feasibility of using low frequency deep brain stimulation of the subthalamic nucleus to improve cognitive performance in patients with Parkinson's disease

risk to the subject. Patients may experience boredom or uncertainty by the cognitive testing.

Neurological Risk:

- There are no risks associated with activating the DBS system on post-operative day 22-24 for participating in this study. There is significant variability in timing of DBS therapy across institutions, with some groups activating the DBS on post-operative day 1 and other groups activating the device on/after post-operative day 30. There are no documented risks associated with the delay between DBS implantation and initiation of therapy.
- Although we expect LFS in the STN to improve cognition based on previous literature, we cannot rule out the possibility that prolonged ventral STN stimulation may temporarily worsen cognition in some patients.

Confidentiality Risk: There is also minimal risk of breach of confidentiality.

18) Potential Benefits to Subjects

There is no direct long lasting benefit to individual subjects. Patients may potentially experience sustained cognitive improvement over a period of time with low frequency stimulation but the duration is currently unknown. Patients may benefit from contributing to our understanding of the neural mechanism underlying cognitive impairment in PD. The information gained in the study will be used to direct treatment plans to improve cognitive impairment in PD and slow the progression of mild cognitive impairment to dementia.

19) Vulnerable Populations

If the research involves individuals who are vulnerable to coercion or undue influence, describe additional safeguards included to protect their rights and welfare.

NA

20) Multi-Site Research

If this is a multi-site study where you are the lead investigator, describe the processes to ensure communication among sites, such as:

NA

21) Community-Based Participatory Research

NA

22) Sharing of Results with Subjects

Describe whether results (study results or individual subject results, such as results of investigational diagnostic tests, genetic tests, or incidental findings) will be shared with subjects or others (e.g., the subject's primary care physicians) and if so, describe how it will be shared.

PROTOCOL TITLE: Safety and feasibility of using low frequency deep brain stimulation of the subthalamic nucleus to improve cognitive performance in patients with Parkinson's disease

Subjects will be given access to their results at the closure of the study. If patients desire, the results of the study will be shared verbally with their treatment team at the Parkinson's clinic. The information will not be shared with any other health care providers.

23) Setting

Describe the sites or locations where your research team will conduct the research.

- *Identify where your research team will identify and recruit potential subjects.*

Specific locations for recruitment will be in the UC Davis Department of Neurosurgery, Department of Neurology and the Ellison Ambulatory Care Center. We will be seeking patients who plan to obtain subthalamic nucleus depth electrodes for Parkinson's disease. We will also recruit patients from Sutter Medical Center and Kaiser Permanente in Sacramento that plan to undergo STN DBS surgery. A newspaper advertisement will allow for recruitment outside of the UC Davis Health network as well.

- *Identify where research procedures will be performed.*

All research procedures and all study visits will take place at UC Davis. For this pilot study, we require the DBS generator adjustment equipment and a quiet exam room for administration of cognitive and motor tests (i.e. ACC clinic exam room or testing room in UC Davis imaging center). The personnel required to consent the subject, administer the tests and analyze the data are sufficient and involve members of the Department of Neurosurgery, Department of Neurology, Department of Psychiatry, UC Davis Imaging Center, UC Davis Clinical and Translational Science Center and the Center for Mind and Brain

- *Describe the composition and involvement of any community advisory board.*

NA

- *For research conducted outside of the organization and its affiliates describe:*

NA

24) Resources Available

Describe your staff and their roles. Describe the qualifications (e.g., training, experience, oversight) required to perform each role. When applicable describe their knowledge of the local study sites, culture, and

PROTOCOL TITLE: Safety and feasibility of using low frequency deep brain stimulation of the subthalamic nucleus to improve cognitive performance in patients with Parkinson's disease

society. Provide enough information to convince the IRB that you have qualified staff for the proposed research.

If you specify a person by name, a change to that person will require prior approval by the IRB. If you specify people by role (e.g., coordinator, research assistant, co-investigator, or pharmacist), a change to that person will not require prior approval by the IRB, provided that person meets the qualifications described above to fulfill their roles.

- Principal Investigator: review of past literature, administration of cognitive tasks, reprogramming DBS generator, analysis of data, recruitment of patients, undergo IRB course(s) for clinical research
- Co-Investigator: administration of cognitive tasks, analysis of data, recruitment of patients, undergo IRB course(s) for clinical research
- Research assistants: administration of cognitive tasks, analysis of data, undergo IRB course(s) for clinical research

Describe other resources available to conduct the research: For example, as appropriate:

- *Justify the feasibility of recruiting the required number of suitable subjects within the agreed recruitment period. For example, how many potential subjects do you have access to? What percentage of those potential subjects do you need to recruit?*

We have access to all patients referred to neurosurgery for implantation of electrodes for intracranial depth electrode seizure monitoring.

- *Describe the time that you will devote to conducting and completing the research.*

3 years

- *Describe your facilities.*

We require the ACC clinic exam rooms or cognitive testing rooms in the UC Davis imaging center for cognitive testing and electrical stimulation.

- *Describe the availability of medical or psychological resources that subjects might need as a result of an anticipated consequences of the human research.*

PROTOCOL TITLE: Safety and feasibility of using low frequency deep brain stimulation of the subthalamic nucleus to improve cognitive performance in patients with Parkinson's disease

Patients will be provided the opportunity to discuss untoward events with the clinical team and any additional consultations medically indicated.

- *Describe your process to ensure that all persons assisting with the research are adequately informed about the protocol, the research procedures, and their duties and functions.*

Each member of the research team will undergo IRB course(s) for clinical research. Each member will be required to read the protocol.

25) Prior Approvals

Describe any approvals that will be obtained prior to commencing the research. (E.g., school, external site, funding agency, laboratory, radiation safety, or biosafety approval.)

NA

26) Provisions to Protect the Privacy Interests of Subjects

Describe the steps that will be taken to protect subjects' privacy interests. "Privacy interest" refers to a person's desire to place limits on whom they interact or whom they provide personal information.

Each member of the team will introduce himself/ herself to the patient and identify his/her involvement in the study.

Describe what steps you will take to make the subjects feel at ease with the research situation in terms of the questions being asked and the procedures being performed. "At ease" does not refer to physical discomfort, but the sense of intrusiveness a subject might experience in response to questions, examinations, and procedures.

The patient will be told that he/she can refuse to participate at any point during the study.

Indicate how the research team is permitted to access any sources of information about the subjects.

The research team will have access to the secured database via password protection.

27) Compensation for Research-Related Injury

The subject should promptly tell the person in charge of the research if they believe that they have been injured because of taking part in this study. If a subject is injured as a result of being in this study, the University of California will provide necessary medical treatment. Depending on the circumstances, the costs of the treatment may be covered by University or the study sponsor or may be billed to your

PROTOCOL TITLE: Safety and feasibility of using low frequency deep brain stimulation of the subthalamic nucleus to improve cognitive performance in patients with Parkinson's disease

insurance company just like other medical costs. The University and the study sponsor do not normally provide any other form of compensation for injury.

28) Economic Burden to Subjects

Describe any costs that subjects may be responsible for because of participation in the research.

NA

29) Consent Process

Indicate whether you will be obtaining consent, and if so describe:

- *Where will the consent process take place:*

Consent will be obtained in the preoperative clinic for UC Davis participants. For Sutter or Kaiser patients, consent will take place at their initial visit to UC Davis.

- *Any waiting period available between informing the prospective subject and obtaining the consent.*

No

- *Any process to ensure ongoing consent.*

Each experimental session will be described to the patient prior to its start, and the patient will be asked permission to proceed with the study.

- *Whether you will be following “SOP: Informed Consent Process for Research (HRP-090) (attach SOP with submission).”*

We will be following HRP-090, Informed Consent Process for Research.

HIPAA Authorization for Research

If the research procedures include accessing personal health information, via the medical records, it is required that subjects sign a HIPAA Authorization for Research form at the time of consent, unless a waiver of informed consent has been granted by the IRB.

For more information on HIPAA Authorization for Research visit the Compliance Program website.

PROTOCOL TITLE: Safety and feasibility of using low frequency deep brain stimulation of the subthalamic nucleus to improve cognitive performance in patients with Parkinson's disease

We will obtain HIPAA authorization. Data files to be stored include group assignment, background information, any head scans if performed, and results from neurocognitive and motor tests. Data files will be stored on secured server through the assistance of the UC Davis Clinical and Translational Science Center, which will be password-protected and access to data files will be given only to IRB-approved research personnel as listed in the research personnel list. For data analysis, each subject will be assigned a unique identification number and there will be no reference to his/her name or any other personal identifier in any subsequent publication. All personal identifiers will be destroyed upon completion of the research and the required storage period. Protected Health Information (PHI) will not be reused or disclosed to any other persons or entity except if subject to an authorized oversight of the research project. Otherwise, the PHI will be protected to the fullest extent possible. Subjects will be given access to their results at the closure of the study. The data and/or specimens will be labeled with a code that the research team can link to personal identifying information when acquired. The code sheet will be secured and kept separate from the dataset.

Non-English Speaking Subjects:

The Consent Short Form will be used for non-English speaking subjects and all UC Davis IRB procedures and policies will be followed.

Waiver or Alteration of the Consent Process (consent will not be obtained, required information will not be disclosed, or the research involves deception)

NA

Subjects who are not yet adults (infants, children, teenagers):

NA

Cognitively Impaired Adults:

NA

Adults Unable to Consent:

NA

Adults Unable to Consent:

NA

PROTOCOL TITLE: Safety and feasibility of using low frequency deep brain stimulation of the subthalamic nucleus to improve cognitive performance in patients with Parkinson's disease

30) Process to Document Consent in Writing

We will be following the “SOP: Written Documentation of Consent (HRP-091)” and have attached the form with submission. We have used the “TEMPLATE CONSENT DOCUMENT (HRP-502)” to create the consent document. We have created written consent forms for both patients and their caregivers.

31) Drugs or Devices: N/A

The deep brain stimulation device is a FDA-approved surgical implant that is normally stored in the Implant Storage Room in the Pavilion Main OR. This storage room is locked. Operating room staff that normally retrieve this device for DBS surgery have keycard access to this room, as do many of the administrative managers in the Pavilion Main OR. The person in charge of ordering and stocking this device for surgical implantation is [name], CNIII.

References

- Colgin LL. 2013. Mechanisms and functions of theta rhythms. Annual review of neuroscience 36: 295-312*

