The protected health information will not be reused or disclosed to any other person or entity, except as required by law, for authorized oversight of the research study, or for other research for which the use of disclosure of PHI for which an authorization or opportunity to agree or object is not required by 45 CFR 164.512. The research could not be practicably conducted without the waiver, and without access and use of the PHI for recruitment.

9) Compensation to the Subjects

Subjects will be compensated \$10 per session. If the patient decides not to participate in further sessions, they will still receive the compensation for the completed sessions. Travel expenses up to \$30 per patient will be provided if needed. The compensation will be in the form of a gift card and will be given at the time of the visit.

PROTOCOL TITLE: Safety and feasibility of using low frequency deep brain stimulation of the subthalamic nucleus to improve cognitive performance in patients with Parkinson's disease

10) Study Timelines

The duration of the study from subject enrollment of the first patient to final data analysis will be approximately two years. Each individual subject will participate in the study for a maximum of 2 months for a total of 3 on-site experimental sessions and one telephone call. The first on-site visit will occur within the month prior to their planned DBS placement surgery, following the pre-operative visit. The second and third on-site visits will occur within the fourth week after the DBS electrode placement surgery, 3-4 days apart. A telephone call will be made 24 hours prior to the third on-site session to obtain additional safety information (Figure 1). Each participant will remain in the study for approximately 2 months from the time of consent. Participation is on a voluntary basis and subjects will reserve the right to withdraw participation in the study at any point of time. We expect the duration to enroll all study subjects will be approximately 2 years based on the number of patients who meet the inclusion and exclusion criteria.

We expect to complete the study by July 2017. The data will be analyzed as individual patients complete the study with further analyses after data collection is complete.

11) Study Endpoints

1. Safety: Safety endpoints will be measured by neuropsychiatric, motor, and cognitive testing:

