a) Neuropsychiatric tests. We will perform the BDI and NPI at baseline, at the first experimental session, once by telephone call after 24 hours of LFS, and a fourth time at the final experimental session. The score of the BDI will be compared across sessions and a score that rises above 20 will be considered positive for the development of moderate depression. The NPI assesses frequency, change in severity, and caregiver distress over 12 neuropsychiatric domains and we will look for caregiver reports of significant change across these domains.

b) Motor tests. The Unified Parkinson's Disease Rating Scale (UPDRS) will be performed prior to patient's surgery as part of the patient's routine care. We will repeat the scale at the final experimental session to assess changes in motor symptoms after sustained LFS.

c) Changes in cognitive function will also be assessed as described below.

2. Feasibility. Improvement in cognitive function will be measured by three cognitive tests: the Stroop test, the N-Back test, and the verbal fluency test. We will measure reaction time and error rates and look for significant changes across stimulator frequencies. The results from 20 patients will help us determine if a large-scale study of effectiveness is warranted and feasible.

Describe any primary or secondary safety endpoints.

See above.

PROTOCOL TITLE: Safety and feasibility of using low frequency deep brain stimulation of the subthalamic nucleus to improve cognitive performance in patients with Parkinson's disease

12) Procedures Involved

a) Describe and explain the study design.

The study design is a safety and feasibility study. We aim to identify 20 PD patients who will receive bilateral STN DBS as part of their standard care. We plan to measure the safety of LFS in the STN as measured through psychological, cognitive, and motor scales, and compare cognitive performance with low and high frequency STN DBS. We propose that LFS in the theta range will not negatively affect psychiatric symptoms or alter motor symptoms, and will improve performance on tests of executive functioning.

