We will also examine changes in psychological symptoms. For each individual patient, we will measure the BDI and NPI at baseline, at the first experimental session, by phone call after 24 h LFS, and at the final experimental session. For the BDI, we will consider any score greater or equal to 20 as evidence of moderate depression and will terminate the study for any individual that shows evidence of depression. At the group level, we will calculate

PROTOCOL TITLE: Safety and feasibility of using low frequency deep brain stimulation of the subthalamic nucleus to improve cognitive performance in patients with Parkinson's disease

the percentage of people that develop depression. For the NPI, we will calculate the total score. At the individual level we will look for the development of new symptoms in the 12 subsections. At the group level we will perform an ANOVA to look for significant changes across the 3 time points.

Cognitive Data Analysis:

The cognitive data analysis will examine the effect of theta frequency stimulation on cognitive task performance. Analyses for the Stroop task will include the examination of response time and error rates across stimulator settings. Two (trial type: congruent vs incongruent) by three (Setting: low, high, no stimulation) ANOVAs will be performed for both reaction time and accuracy. Post conflict and post error reaction time adjustments will also be examined across stimulator settings. For the N-back test, ANOVAs will also be performed to assess the effects of complexity (1,2-back) and stimulation frequency (none, high, low) on error rates. For the verbal fluency test, the average number of words generated across stimulation conditions and the change in word number on low and high frequency stimulation settings will be compared. Analyses will be performed using MATLAB and STATA.

Describe any procedures that will be used for quality control of collected data.

a.) Study-Wide:

NA

b.) Local

Describe the local procedures for maintenance of confidentiality.

This research is partly funded by a donation from the Chevo Foundation. The Chevo Foundation will not have access to any of the study documents including the data.

Data files to be stored include group assignment, background information, any head scans if performed, and results from neurocognitive and motor tests.

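### Cognition is a safety endpoint, but the planned analysis has no per-patient measure or count of cognitive worsening and does not name the 48-hour sustained-LFS battery

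*Combined protocol and SAP*

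**What the plan says.** Aim 1 in section 4 includes the cognitive consequences of LFS among the safety questions. Section 11 opens with "Safety endpoints will be measured by neuropsychiatric, motor, and cognitive testing". Item 1c, the cognitive part, reads in full "Changes in cognitive function will also be assessed as described below". The item that follows is Feasibility, and it is worded as benefit: "Improvement in cognitive function will be measured by three cognitive tests: the Stroop test, the N-Back test, and the verbal fluency test".

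Section 14 has two analysis subheadings. Its Safety Data Analysis covers the UPDRS motor section, the BDI and the NPI. Its Cognitive Data Analysis specifies "Two (trial type: congruent vs incongruent) by three (Setting: low, high, no stimulation) ANOVAs" for Stroop reaction time and accuracy, ANOVAs of N-back errors over the same three settings, and a comparison of word counts and their change for verbal fluency with no test named. Post-conflict and post-error adjustments are to be examined across settings.

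Section 15 says "Safety data will include performance on psychological screening tests, cognitive tests, and motor tests", and the next sentence adds "Efficacy data will include performance on cognitive tests". Its own safety analysis includes cognition by reference back: "Changes in cognition will also be analyzed by looking at reaction time and error rates on different cognitive tests as described previously".

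Section 17 states the risk: "we cannot rule out the possibility that prolonged ventral STN stimulation may temporarily worsen cognition in some patients".

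**The concern.** The stated risk concerns some patients under prolonged stimulation. The written analysis addresses neither part of it. It compares settings across the group, and its settings are low, high and none; the 48-hour battery at the second experimental session (E2) is collected under section 12 but is not named as a level.

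Section 4 also says that negative effects on performance will be picked up before further patients are tested. No direction of harm, individual change or count is defined that would show whether this had happened. At stake is the cognitive part of Aim 1: the trial could report no cognitive harm from a group comparison in which a few patients with marked decline are offset by the others.

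**Working it through.** **1. The three safety domains side by side (sections 14 and 15)**

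| Domain | Individual-level step | Limit | Count of affected patients | Group analysis |
|---|---|---|---|---|
| Motor (UPDRS) | Individual change after each patient | None | None | t-test |
| Mood (BDI) | Score checked for each patient | 20 or more | Percentage developing depression | ANOVA (section 15) |
| Neuropsychiatric (NPI) | New symptoms in 12 domains | None | None | ANOVA |
| Cognition | None stated | None | None | Comparisons across low, high, none |

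Cognition is the only row with no individual-level step.

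**2. Can a group comparison average away a harmed minority?**

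The plan gives no figure to reproduce: it states no alpha, SD, effect size or rate of cognitive harm. The analysed sample is 22 − 2 = 20, since two subjects only try out the computer test.

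Assumptions: within-patient changes have SD 1 around each patient's true change; k of 20 patients worsen by 2 SD; the others change by g SD; the test is one two-sided 5% paired t-test. This stands in simply for the planned ANOVAs.

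For k = 3 and g = 0:
- Mean true change = 3 × (−2) / 20 = −0.30 SD.
- The mixture also inflates the spread. The variance of the true changes is (3 × 17 × 2²) / (20 × 19) = 0.537, so the observed SD is about √(1 + 0.537) = 1.24.
- Standard error = 1.24 / √20 = 0.277, so the typical t is about −0.30 / 0.277 = −1.08, against a critical value of −2.09 on 19 df.

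Simulated share of trials showing significant worsening:

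| Patients worse by 2 SD | Others unchanged | Others improve by 0.3 SD |
|---|---|---|
| 2 of 20 | 8% | 0.4% |
| 3 of 20 | 13% | 1% |
| 4 of 20 | 20–21% | 2% |

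The right-hand column adds an assumed benefit in the other patients, so the middle column is the fairer illustration. With 4 of 20 worsening by only 1 SD and the rest unchanged, the share is 10%.

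**3. What a per-patient count would show**

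On one measure with a one-sided 2.5% limit (1.96 SD), a patient truly 2 SD worse is flagged with probability Φ(2 − 1.96) = 0.52. At least one of three such patients is flagged with probability 1 − 0.48³ = 0.89.

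The count would be imprecise. Exact 95% intervals with n = 20 are 0 to 16.8% for 0 patients, 0.1 to 24.9% for 1, 1.2 to 31.7% for 2, and 5.7 to 43.7% for 4.

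**4. Chance flags**

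Four measures (Stroop reaction time, Stroop errors, N-back errors, FAS words) at two time points (acute and sustained LFS) make 8 comparisons per patient. Among 20 unaffected patients, expected flags = 20 × 8 × 0.025 = 4. If the comparisons were independent, the share of patients flagged at least once would be 1 − 0.975⁸ = 18%, or about 3.7 of 20.

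**The case against.** A reader might infer that patients who decline would go unseen. The documents do not support that. Section 10 has data analysed as patients complete the study. Section 15 has the investigators review data after every visit and call, and a safety committee that includes an expert in neurocognitive assessment reviews after 4, 8, 12 and 20 patients. Section 16 withdraws patients who cannot perform the tests. A marked decline may well be noticed. What is missing is a definition and a count in the planned analysis; inability to perform a test is not the same as a decline in score.

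A reader might also infer that the sections contradict each other on whether cognition is safety. They do not. Section 14 puts cognition under its own subheading and section 15 refers back to it. Nor is the analysis purely ANOVA: fluency and the reaction-time adjustments have no named test. They too are compared across settings with no patient-level step.

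It is fair to say that the motor endpoint has no limit or count either. Strict parity would require only individual changes. The limit and count go further, and rest on section 17 describing harm in some patients.

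The simulation has its own limits. Its inputs are assumed, and it says nothing about the early cohort reviews, where no significance test is planned.

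**Conclusion.** The point holds as a gap in the planned analysis. Cognition is a declared safety endpoint without a per-patient change, a direction of harm or a count, and the sustained-LFS battery, the exposure closest to the stated risk, is outside every named comparison. Following the text, cognitive safety would be judged on group comparisons that can miss a harmed minority: about 8% to 21% of trials would show significant worsening if 2 to 4 of 20 patients declined by 2 SD and the rest did not change. Those figures rest on an assumed SD, effect and test, and illustrate the mechanism only. Informal review reduces the practical risk, so this is a cheap improvement worth making rather than a flaw that invalidates the trial.

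**What to change.** In the Safety Data Analysis of both section 14 and section 15, add:

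- For each patient, calculate the change in Stroop reaction time, Stroop errors, N-back errors and FAS words from the no-stimulation battery at the first experimental session (E1) to the acute LFS battery, and to the sustained-LFS battery at E2.
- For each measure and time point, report the number and percentage of patients worse than a limit fixed in advance by the investigators, with an exact 95% CI.
- Include this table in the 4-, 8-, 12- and 20-patient reviews, beside the individual UPDRS, BDI and NPI results.
- State that practice or fatigue may bias the changes in either direction. The batteries are repeated in sequence, and the documents do not establish which effect dominates.

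The cost is analysis wording and one table per review, from data already collected. The downside is about 4 chance flags in 20 unaffected patients at a one-sided 2.5% limit, similar in number to the harmed minority illustrated above. The table should therefore be labelled descriptive. Any clinical response to a flagged decline is for the investigators to decide.
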